^c Cabozantinib will be discontinued on the single-agent cabozantinib arm if a qd dose of 20 mg cabozantinib is not tolerated

Table 8: Dose Modifications for Cabozantinib-Related AEs

CTCAE v5 Grade	Recommended Guidelines for Management ^a
Grade 1 AEs	Add supportive care as indicated. Continue cabozantinib at the current dose level if AE is manageable and tolerable.
Grade 2 AEs which are tolerable and are easily managed	Continue cabozantinib at the current dose level with supportive care.
Grade 2 AEs which are intolerable and cannot be adequately managed	Cabozantinib should be dose reduced or interrupted. Note: It is recommended that dose interruptions be as brief as possible.
Grade 3 AEs (except clinically non-relevant laboratory abnormalities)	Cabozantinib should be interrupted unless the toxicity can be easily managed with a dose reduction of cabozantinib and optimal medical care. Note: It is recommended that dose interruptions be as brief as possible.
Grade 4 AEs (except clinically non-relevant laboratory abnormalities)	Cabozantinib must be interrupted immediately. In general, cabozantinib should be discontinued unless the following criteria are met: 
• Subject is deriving clear clinical benefit as determined by the investigator and agreed by the Sponsor• Toxicity can be managed with a dose reduction of cabozantinib following recovery to Grade 1 (or baseline) and optimal medical care Sponsor must be contacted to discuss treatment continuation upon resolution of AEs.

AE, adverse event.

Note: Cabozantinib dose modification criteria for specific medical conditions are provided in [Section 6.6.2.1](#).

Atezolizumab:

- The assigned dose for atezolizumab is 1200 mg IV every 3 weeks. Infusion will occur every three weeks (\pm 2 days).
- Dose delays are allowed for atezolizumab (see [Table 9](#)), but dose reductions are not allowed.
- Dose modification criteria for irAEs and other AESIs and for guidance on reinstating atezolizumab are shown in [Table 10](#).
- If corticosteroids are initiated for treatment of irAEs, they must be tapered over \geq 1 month to \leq 10 mg/day oral prednisone or equivalent before atezolizumab can be resumed.
- Guidelines for the management of IRRs and CRS, irAEs for atezolizumab (ie, pneumonitis, hepatitis, diarrhea/colitis, myocarditis, endocrinopathies including hypophysitis, and infection) and other AESIs are provided in [Section 6.6.2.2](#).

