Table 9: Dose Interruptions of Atezolizumab

Assigned dose	Dose Interruptions
1200-mg atezolizumab IV q3w	At any time to manage unacceptable AESIs

AESI, adverse events of special interest; q3w, once every 3 weeks;

Table 10: Dose Modifications for Atezolizumab-Associated Adverse Events

CTCAE v5 Grade	Recommended Management
Grade 1 immune-mediated myelitis*	Delay treatment with atezolizumab
Grade 1 pericarditis**	Treatment may be resumed in subjects following recovery to Grade 0-1
Grade 2 myocarditis	
Grade 1 ^a - 2 pneumonitis	* Continue atezolizumab unless symptoms worsen or do not improve.
Grade 2 nephritis	
Transaminases (ALT or AST):	** Withhold treatment with atezolizumab and conduct a detailed cardiac evaluation to determine the etiology and manage accordingly.
• Increases to between $> 3 \times$ ULN and $\leq 10 \times$ ULN (from baseline values \leq ULN), or	
• Increases to between $> 5 \times$ ULN and $\leq 10 \times$ ULN (from baseline values between $>$ ULN and $\leq 3 \times$ ULN), or	
• Increases to between $> 8 \times$ ULN and $\leq 10 \times$ ULN (from baseline values between $> 3 \times$ ULN and $\leq 5 \times$ ULN)	

CTCAE v5 Grade	Recommended Management
Grade 2 immune-mediated neuropathy (any cranial nerve disorder, including facial paresis, should be managed as per Grade 2 guidelines)***	Delay treatment with atezolizumab Treatment may be resumed in subjects following recovery to Grade 0-1.
Grade 2 or 3 diarrhea or colitis	
Grade 2 or 3 myositis	
Symptomatic adrenal insufficiency, hypothyroidism, or hyperthyroidism; Grade 2 or 3 hypophysitis; or Grade 3 or 4 hyperglycemia	*** For general immune-related neuropathy, if the event resolves to Grade 1 or better, resume atezolizumab. For facial paresis, if event resolves fully, resume atezolizumab; if event does not resolve fully while withholding atezolizumab, permanently discontinue atezolizumab.
Grade 2 ocular inflammatory toxicity	
Grade 2 or 3 pancreatitis or Grade 3 or 4 increases in amylase or lipase levels	
Grade 3 or 4 infection	
Grade 2 infusion-related reactions or cytokine release syndrome	
Grade 3 rash	
Suspected Stevens-Johnson syndrome or toxic epidermal necrolysis (any grade)	
Other Grade 2 or 3 atezolizumab-associated AEs	
Grade 2 - 4 immune-mediated myelitis	Permanently discontinue atezolizumab
Grade 3 or 4 immune-mediated neuropathy, including facial paresis	
Grade 2 - 4 myocarditis	
Grade 4 myositis and/or recurrent Grade 3 myositis	
Grade 3 or 4 pneumonitis	

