Grade 3 or 4 nephritis	
AST or ALT $> 10 \times$ ULN or total bilirubin $> 3 \times$ ULN	
Grade 4 diarrhea or colitis	
Grade 4 hypophysitis and/or recurrent hypophysitis	
Myasthenic syndrome/myasthenia gravis, Guillain-Barré or meningoencephalitis (all grades)	
Grade 3 or 4 ocular inflammatory toxicity	
Grade 4, or recurrent Grade 2 or 3, immune-mediated pancreatitis	

CTCAE v5 Grade	Recommended Management
Grade 3 or 4 infusion-related reactions or cytokine release syndrome	
Grade 4 rash	
Confirmed Stevens-Johnson syndrome or toxic epidermal necrolysis (any grade)	
Other Grade 4 or recurrent Grade 3 atezolizumab-associated AEs	Permanently discontinue atezolizumab

AE, adverse event; AESI, adverse events of special interest; ALT, alanine aminotransferase; AST, aspartate aminotransferase; irAE, immune-related adverse event; ULN, upper limit of normal.

Note: Additional information for atezolizumab dose modification criteria and treatment recommendations for irAEs, infusion reactions, and other AESIs are provided in [Section 6.6.2.2](#).

^a Consider interrupting atezolizumab for Grade 1 pneumonitis.

^b Resumption of atezolizumab may be considered in patients who are deriving benefit and have fully recovered from the immune-mediated event. The decision to re-challenge patients with atezolizumab should be based on investigator's assessment of benefit–risk and documented by the investigator. The Medical Monitor is available to advise as needed.

Sorafenib:

- The assigned dose for sorafenib is 400 mg twice daily.
- When dose reduction is necessary, the sorafenib dose may be reduced to 400 mg once daily (qd). If additional dose reduction is required, sorafenib may be reduced to a single 400 mg dose every other day (qod).

For additional details on management guidance of AEs refer to the most current sorafenib prescribing information appropriate to the respective site location.

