6.6.2.2.7. Immune-Related Meningoencephalitis

Immune-related meningoencephalitis is an identified risk associated with the administration of atezolizumab. Immune-related meningoencephalitis should be suspected in any subject presenting with signs or symptoms suggestive of meningitis or encephalitis, including, but not limited to, headache, neck pain, confusion, seizure, motor or sensory dysfunction, or altered or depressed level of consciousness. Encephalopathy from metabolic or electrolyte imbalances needs to be distinguished from potential meningoencephalitis resulting from infection (bacterial, viral, or fungal) or progression of malignancy, or secondary to a paraneoplastic process.

All subjects being considered for meningoencephalitis should be urgently evaluated with a CT scan and/or MRI scan of the brain to evaluate for metastasis, inflammation, or edema. If deemed

safe by the treating physician, a lumbar puncture should be performed and a neurologist should be consulted.

Subjects with signs and symptoms of meningoencephalitis, in the absence of an identified alternate etiology, should be treated according to the guidelines in [Table 20](#).

Table 20: Management Guidelines for Immune-Related Meningoencephalitis

Severity of Event	Management
All grades	
• Permanently discontinue atezolizumab and contact the Sponsor ^a• Refer subject to neurologist• Initiate treatment with 1–2 mg/kg/day IV methylprednisolone or equivalent and convert to 1–2 mg/kg/day oral prednisone or equivalent upon improvement• If event does not improve within 48 hours after initiating corticosteroids, consider adding an immunosuppressive agent• If event resolves to Grade 1 or better, taper corticosteroids over \geq 1 month

IV, intravenous.

^a Resumption of atezolizumab may be considered in subjects who are deriving benefit and have fully recovered from the immune-related event. The decision to rechallenge with atezolizumab should be based on investigator's assessment of benefit-risk, and documented by the investigator. The Medical Monitor is available to advise as needed.

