6.6.2.2.14. Other Atezolizumab-Associated Immune-Related Adverse Events

The following general management guidance should be applied for any other atezolizumab-associated irAEs:

- Grade 2 or 3: delay atezolizumab dosing up to 12 weeks until irAE recovers to Grade 0-1 and corticosteroids have been reduced to ≤ 10 mg prednisone or equivalent per day
- Grade 4 or recurrent Grade 3: permanently discontinue atezolizumab

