- Grade 4: Life-threatening consequences; urgent intervention indicated
- Grade 5: Death

Management of Hepatic Encephalopathy

In patients with HE, the first step in management is to identify and treat the precipitating factors for HE including, but not limited to, diarrhea, vomiting, decreased appetite, electrolyte abnormalities, infections, GI bleeding, diuretic overdose, and constipation.

The following treatments are recommended (Vilstrup et al 2014):

- For symptomatic patients, consider treating with lactulose.
- After the initial episode, lactulose is recommended for prevention of recurrent episodes of HE.
- After the second episode, rifaximin is recommended as an add-on to lactulose for prevention of recurrent episodes of HE.
- Intravenous (IV) L-ornithine L-aspartate (LOLA) and branched-chain amino acids (BCAAs) can be used as an alternative or additional agent to treat patients nonresponsive to conventional therapy.
- Neomycin and metronidazole are alternative choices for treatment.

For patients with higher grades (\geq Grade 3) HE, consider hospitalization. Patients who are at risk or unable to protect their airway need more intensive monitoring and are ideally managed in an intensive care setting. Please refer to Vilstrup et al 2014 for further information. Detailed guidelines for the management of HE are provided in [Table 30](#).

Table 30: Management of Hepatic Encephalopathy Associated with Study Treatment

Hepatic Encephalopathy	
CTCAE v5.0 Grade	Recommended Guidelines for Management and Dose Modification
Grade 1	
Identify and treat any precipitating factor.
 
If symptomatic, consider treatment for AEs.
 
Continue study treatment if asymptomatic and an AE is manageable and tolerable.

Grade 2	
Consider treatment for AEs.
 
Continue study treatment if an AE is manageable and tolerable or interrupt study treatment for grade 2 AEs that are intolerable or cannot be adequately managed.
 
If an irAE is suspected, consider initiating steroid treatment.

Grade 3	
Consider hospitalization.
 
If an irAE is suspected, consider initiating steroid treatment.
 
Interrupt study treatment; Sponsor must be contacted to discuss treatment continuation upon resolution of AEs.
 
Study treatment may resume if the toxicity can be easily managed with a dose reduction and optimal medical care.

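### Table 30, Grade 2 hepatic encephalopathy: a suspected immune-related cause is not tied to holding atezolizumab, unlike Table 10, Table 20 and Section 6.6.2.2.14

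*Protocol*

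**What the plan says.** Table 30 in Protocol Section 6.6.2.4 sets dosing for hepatic encephalopathy (HE) by CTCAE grade. The Grade 2 row reads "Continue study treatment if an AE is manageable and tolerable or interrupt study treatment for grade 2 AEs that are intolerable", and it also interrupts for events that cannot be controlled well enough. The rule covers study treatment as a whole, so in the experimental arm it covers atezolizumab. The row adds "If an irAE is suspected, consider initiating steroid treatment" and nothing more on the immune question. The text before the table asks sites to look for other causes of altered mental status, irAEs among them, and gives meningoencephalitis as the example.

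The atezolizumab rules elsewhere are firmer:

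- Table 10 (Section 6.6.1) places "Other Grade 2 or 3 atezolizumab-associated AEs" among the events for which atezolizumab is delayed until recovery to Grade 0-1.
- Section 6.6.2.2.14, for irAEs without their own table, says "Grade 2 or 3: delay atezolizumab dosing up to 12 weeks until irAE recovers to Grade 0-1", with steroids also reduced to 10 mg prednisone equivalent per day or less.
- Table 10 lists meningoencephalitis of every grade under permanent discontinuation, and Table 20 (Section 6.6.2.2.7) gives the same instruction.

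**The concern.** HE and immune-related meningoencephalitis can look alike: confusion and altered consciousness appear in the protocol's description of each. The protocol also says that no specific test diagnoses HE. A site that grades an event as Grade 2 HE will open Table 30. If the subject is coping, that row permits treatment to go on, and suspicion of an irAE brings only an optional steroid. The site could therefore give the next infusion while an immune cause, possibly meningoencephalitis, is still being worked up. What is at stake is the safety of subjects in the experimental arm during that work-up.

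**Working it through.** No published figure needs reproducing, so the check is a comparison of the rules, followed by subtraction of what other rules already cover.

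1. **Table 30, rows with an irAE line.** These are Grades 2, 3 and 4, so three rows. Grade 3 interrupts study treatment and Grade 4 discontinues it. Grade 2 continues or interrupts according to tolerability. One row of three lets treatment continue with an irAE suspected.

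2. **The same subject under each rule (Grade 2, irAE suspected).**
   - Table 30: may continue; consider steroids.
   - Table 10 and Section 6.6.2.2.14: delay atezolizumab, if the event is treated as atezolizumab-associated.
   - Tables 10 and 20: stop atezolizumab permanently, if the event is treated as meningoencephalitis.

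3. **Does the protocol act on suspicion elsewhere?** Yes. Tables 10 and 18 withhold atezolizumab for suspected Stevens-Johnson syndrome or toxic epidermal necrolysis. Table 27 stops it permanently for suspected hemophagocytic lymphohistiocytosis or macrophage activation syndrome. A hold during work-up is consistent with the sponsor's own approach.

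4. **What other rules already cover.**
   - Steroids started: Section 6.6.1 says "If corticosteroids are initiated for treatment of irAEs, they must be tapered over" at least a month, to 10 mg/day or less, before atezolizumab resumes. Section 7.1 agrees.
   - Recurrent events, or events lasting more than 5 days: Section 6.6.2.2 treats these Grade 2 events as Grade 3, and holds atezolizumab at Grade 3.
   - No infusion due: doses are 3 weeks apart, within 2 days either way (Section 6.2.4), and never less than 19 days apart (Section 5.2).

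5. **What is left.** All of these must hold together: Grade 2, an irAE suspected but the cause unresolved, no steroids, a first episode of 5 days or less, and an infusion falling inside it. As a guide to the last condition only, assume that onset is equally likely on any day between infusions. The share of onsets within 5 days before an infusion is 5/21 = 0.24, or 5/23 = 0.22 to 5/19 = 0.26 across the allowed spacing. Events that resolve before the infusion lower this. It is a share of onset times, not a rate of cases.

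**The case against.** The strongest reply is that the protocol already protects this subject. Table 20 needs no confirmed diagnosis: "Subjects with signs and symptoms of meningoencephalitis, in the absence of an identified alternate etiology, should be treated according to the guidelines in" that table, and while the work-up is open it can be argued that no other cause has been found. Section 6.6.2.2.7 adds "All subjects being considered for meningoencephalitis should be urgently evaluated with a CT scan and/or MRI scan of the brain". Section 6.6.1 lets the investigator interrupt either agent at any time and leaves unclear attribution to judgment. Section 6.6.2.2 says to consider holding for most Grade 2 toxicities and to weigh benefit and risk before further atezolizumab.

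Much of this stands, and it is why the gap is small. It does not close it. The discretionary clauses allow a hold without requiring one. Whether Table 20 is triggered is open to reading: a site using Table 30 already has HE as a candidate explanation, and Table 30 does not send it to Table 20.

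A reader might infer that Table 30 tells sites to continue atezolizumab despite a suspected irAE. It does not. It permits continuation for a tolerated event, provides for interruption in the same sentence, and simply leaves suspicion unconnected to any hold.

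A reader might also infer that the Grade 1 row needs correcting, because it allows continuation only without symptoms while Grade 1 is defined by mild symptoms. The documents do not support a change. The row contains no order to interrupt, Table 8 and the Section 6.6.1 text on mild events cover a symptomatic subject, the HE text recognizes subclinical forms, and the mismatch errs toward caution.

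Nor is there a real conflict in the hepatic-failure text. The Grade 4 stop is specific and controls, and Grade 3 hepatic failure is also covered by Tables 8 and 10. Relaxing the Grade 1 row and also declaring that Table 30 governs Grade 3 hepatic failure would create a continue instruction for mild encephalopathy in that setting.

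**Conclusion.** The point holds in a limited form. The Grade 2 row of Table 30 is more permissive than the atezolizumab rules it should point to, for a short window before the cause is settled and without steroids. The conclusion rests on two readings: that study treatment in Table 30 includes atezolizumab, and that a site facing Grade 2 encephalopathy will work from Table 30.

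No number of affected subjects can be given, because the documents report no rate for HE with a suspected irAE. It is tempting to multiply the 0.4% meningoencephalitis rate quoted for atezolizumab monotherapy in Section 6.6.2.4 by the 370 planned experimental subjects (0.004 × 370 = 1.48). That would count every expected case of meningoencephalitis, not those that fall in this window, so it does not measure the gap.

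This is a cheap improvement for patient safety. It does not touch any endpoint, alpha or power.

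**What to change.** In the Grade 2 row of Table 30, add: *If an irAE is suspected, withhold atezolizumab pending evaluation and follow Table 10, Table 20 or Section 6.6.2.2.14 as applicable.* In the Grade 3 row, which already interrupts treatment, add only the cross-reference. Leave the Grade 1 and Grade 4 rows and the hepatic-failure text as they are.

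The cost is wording in one protocol section and a memo to sites, with no added procedures or subjects. The clinical downside is a possible short atezolizumab delay in a subject whose event turns out to be non-immune HE.

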7. CONCOMITANT MEDICATIONS AND THERAPIES

7.1. Allowed Therapy

- Antiemetics and antidiarrheal medications are allowed prophylactically according to standard clinical practice if clinically indicated.
- Granulocyte colony-stimulating factors (G-CSF or GM-CSF) are allowed if used per clinical guidelines (eg, ASCO or ESMO guidelines).
- Bisphosphonates can be used per standard of care if the benefit outweighs the risk per the Investigator's discretion ([Section 6.6.2.1.8](#)).

Note: osteonecrosis of the jaw has been reported in subjects using bisphosphonates. Oral examinations are recommended at screening to determine eligibility and periodically during the study. In addition, subjects should be advised regarding oral hygiene practice and to quickly report symptoms to the Investigator. Frequent monitoring for potentially overlapping toxicities with study treatment is recommended.

- Transfusions and hormone replacement should be utilized as indicated by standard clinical practice.
- Inhaled, intranasal, intra-articular, or topical corticosteroids are allowed if minimal systemic absorption. Systemic corticosteroids are allowed for control of infusion reactions or irAEs and must be tapered over ≥ 1 month to a dose level ≤ 10 mg/day of prednisone equivalent before next atezolizumab administration. Prophylactic steroid treatment for subjects with contrast allergies prior to tumor imaging is allowed, and short term treatment with systemic corticosteroids for acute medical conditions (eg, exacerbation of chronic obstructive pulmonary disease [COPD]) is allowed if clinically indicated.
- Individualized anticoagulation therapy with heparin is allowed if it can be provided safely and effectively under the following circumstances:
 - *Low dose LMWH for prophylactic use* are allowed if clinically indicated and the benefit outweighs the risk per the investigator's discretion.
 - *Therapeutic doses of LMWH after first dose of study treatment* are allowed if clinically indicated (eg, for the treatment of DVT), and the benefit outweighs the risk per the

investigator's discretion. For management of thromboembolic complications while on study, refer to [Section 6.6.2.1.4](#).

- Accepted clinical guidelines regarding appropriate management while receiving anticoagulation therapy with heparins must be followed. This includes, but is not limited to, subject education regarding potential adverse drug reactions, monitoring laboratory parameters, dose adjustments (eg, due to kidney dysfunction, platelet decrease).
- For restrictions on oral anticoagulants see [Section 7.2](#).
- Considerations for use of COVID-19 vaccine: At this time, there are limited data available for the use of COVID-19 vaccines in specific subsets of individuals such as the immunocompromised and cancer patients, including those receiving anticancer therapies such as cabozantinib, atezolizumab, and sorafenib. The decision to proceed with vaccination for subjects enrolled in this clinical study rests with the treating physician and the subject and should be taken after consideration of all safety precautions provided by the manufacturers of the vaccines and local health authorities. Please note, immunizations with live, attenuated COVID-19 vaccines or any experimental vaccines are not allowed. Exelixis will monitor all available information and provide additional guidance as appropriate.

Potential drug interactions with cabozantinib, atezolizumab, and sorafenib are summarized in [Section 7.3.1](#), [Section 7.3.2](#), and [Section 7.3.3](#), respectively.

7.2. Prohibited or Restricted Therapy

The following therapies are prohibited until study treatment has been permanently discontinued:

- Any investigational agent or investigational medical device.
- Therapeutic doses of oral anticoagulants (eg, warfarin or other coumarin-related agents, direct thrombin or direct FXa inhibitors, or antiplatelet agents such as clopidogrel, or chronic use of aspirin above low dose levels for cardioprotection per local applicable guidelines).
- Any nonprotocol systemic anticancer treatment (eg, chemotherapy, immunotherapy, radionuclides, drugs or herbal products used specifically for the treatment of the cancer under investigation).

- Concomitant use of denosumab with atezolizumab is prohibited due to a potential for increased risk of infections.
- Immunosuppressive agents including immunosuppressive doses of systemic corticosteroids with exceptions as stated in [Section 7.1](#).
- Metamizole (dipyrone) because of its potential for causing agranulocytosis.

The following therapies should be avoided until study treatment has been permanently discontinued or until otherwise specified:

- Local anticancer treatment including palliative radiation, ablation, embolization, or surgery with impact on tumor lesions should not be performed until radiographic progression per RECIST 1.1 has been established. If clinically unavoidable the investigator should consult the Sponsor prior to the procedure for safety guidance.
- Erythropoietic stimulating agents (eg, epoetin alfa and darbepoetin alfa) should not be used based on a report of increased risk of tumor recurrence/progression associated with erythropoietin (Wright et al 2007).
- Concomitant medications that are known to prolong the QTc interval should be avoided in subjects until they have permanently discontinued cabozantinib or sorafenib treatment (refer to <http://www.qtdrugs.org> for a list of drugs which have the potential to prolong the QTc interval).
- Live vaccines are prohibited while on study and until 5 months after last atezolizumab dose (eg, intranasal influenza, measles, mumps, rubella, oral polio, Bacillus Calmette-Guérin, yellow fever, varicella, and TY21a typhoid vaccines). The use of inactivated (killed) vaccines for the prevention of infectious disease requires Sponsor approval with the exception of an inactivated influenza vaccine, which can be given without Sponsor approval.
- Chronic co-administration of cabozantinib or sorafenib with strong inducers of the CYP3A4 family (eg, phenytoin, carbamazepine, rifampin, rifabutin, rifapentine, phenobarbital, and St. John's Wort) may significantly decrease concentrations of these study drugs and should be avoided. Selection of alternate concomitant medications with no or minimal CYP3A4 enzyme induction potential is recommended.

- Caution must be used when discontinuing treatment with a strong CYP3A4 inducer in a subject who has been concurrently receiving a stable dose of cabozantinib or sorafenib, as this could significantly increase the exposure to these study drugs.
- Co-administration of cabozantinib with strong inhibitors of the CYP3A4 family (eg, boceprevir, conivaptan, posaconazole, ketoconazole, itraconazole, clarithromycin, atazanavir, indinavir, nefazodone, nelfinavir, saquinavir, ritonavir, lopinavir, telaprevir, telithromycin, and voriconazole) may increase concentrations of study drug and should be avoided. Grapefruit, star fruit, and Seville oranges may also increase plasma concentrations of these study drugs and should be avoided.

Additional information on potential drug interactions with cabozantinib, atezolizumab, and sorafenib are summarized in [Section 7.3.1](#), [Section 7.3.2](#), and [Section 7.3.3](#), respectively.

